(3). The collective process yielded a novel wheelchair exercise training program that is ready to be examined for feasibility before testing within a formal clinical trial.

- Ultimately, this study extends [name] line of research and may initiate a significant paradigm shift in rehabilitation research and practice by providing a critically needed home-based exercise training program for enhancing health, quality of life, participation, and independence of wheelchair user with MS.

Objectives

- To examine the feasibility, acceptability, and initial efficacy of a stakeholder-informed, home-based, remotely supported and supervised exercise training program for wheelchair users with multiple sclerosis (MS) compared to an attention/contact wellness control program.
- Feasibility will be operationalized using ongoing assessment of recruitment, retention, and safety. We hypothesize that the intervention will be feasible in terms of reaching recruitment goals (n=24; 12 per group) within a one-year period, retaining ≥80% of those participants through the full 16-week study period, and safe in terms of <10% of participants reporting adverse events. We are defining our recruitment goals as participants who matriculate and are randomized, therefore we aim to consent up to 28 participants.

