- Acceptability will be operationalized as participant satisfaction and perceptions measured in post-intervention formative surveys and interviews. We hypothesize that a greater proportion of participants in the SPIN exercise training condition will report high satisfaction and positive perceptions regarding the exercise training program compared with the attention/contact wellness control condition.
- The study will further examine changes in scientific outcomes of interest (i.e., metabolic health, MS symptoms, and exercise behavior change) for determining effect size and sample size estimates in powering a larger clinical trial. We hypothesize that the SPIN exercise training intervention program will lead to greater improvements in metabolic health outcomes (i.e., HbA1c, cholesterol, glucose, and triglycerides), MS symptoms (i.e., fatigue, pain, depression, and quality of life) and exercise behavior compared to the attention/control wellness program.

Study Design

- Parallel group, randomized controlled trial

- The study is funded for a 2 year period and participants will be involved in study procedures for approximately 6 months.
- The primary outcome of interest is feasibility (i.e., recruitment, retention, and safety). The secondary outcome of interest is acceptability (i.e., participant satisfaction and perceptions).
- The tertiary outcomes of interest are scientific outcomes of initial efficacy(i.e., metabolic health, MS symptoms, and exercise behavior).
- Safety will be assessed in terms of incidence of participants reporting adverse events.

Study Population

- Eligibility criteria: (a) diagnosis of MS; (b) self-reported use of a wheelchair (i.e., manual wheelchair, power wheelchair, or scooter) ≥50% of the time; (c) age of 18 years or older; (d) relapse free for the past 30 days; and (e) being non-active defined as not engaging in regular physical activity (30 minutes accumulated per day) on more than 2 days of the week during the previous 6 months (i.e., not meeting current physical activity guidelines for MS). During telephone screening participants will complete an exercise pre-participation health screen and if participants report any symptoms or conditions contradictory of exercise then physician clearance will be required before enrollment.

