- All testing will be performed by trained personnel and all equipment will be calibrated daily before testing. If an individual indicates discomfort or the desire to discontinue testing, tests will be terminated immediately. All adverse events will be reported to the UTHealth Houston IRB and reviewed by the investigative team. Should any of these individuals and/or the IRB identify that any adverse event may be related to the study protocol, testing will be suspended and the protocol will be amended accordingly. Adverse events will be tracked using a REDCap database for assessing the primary study outcomes.

Statistics

- The planned enrolled sample size of 28 participants (i.e., 12 per group that matriculate and are randomized) is justified for pilot clinical trials when there is no prior information for sample size estimation.
- [name] (PI) will lead the data analyses given her expertise in both quantitative and qualitative data analyses. Participant characteristics will be reported using means/medians and standard deviations/interquartile ranges for continuous variables. Categorical measures will be presented as counts and percentages. The analysis will use the intent-to-treat principle where patients will be

analyzed in their randomization assignment. Descriptive statistics including frequencies and percentages will be utilized to assess the feasibility metrics for the primary and secondary outcomes (*Hypothesis 1 & Hypothesis 2*). The scientific outcomes in *Hypothesis 3* (i.e., metabolic health outcomes, MS symptoms, and exercise behavior) will be examined using 2 time by 2 group mixed factor ANOVA with estimation of Cohen's d values for effect sizes. Participant's change in scientific outcomes will be further examined and compared with the ≥ 0.5 SD will be considered meaningful change based on benchmarks established in previous research.

Ethics

- First, following screening all participants deemed eligible for the study will then be sent a consent form to review and sign using through REDCap. The PI will review the consent document to ensure participants understand study procedures and sign the document prior to enrollment. During consent process the research team will emphasize the voluntary nature of all research procedures and assess consent at each following contact as consent is an ongoing process.

Data handling and record keeping

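### The effect sizes meant to size a larger trial are planned as uncorrected Cohen's d, with no analysis scale stated for triglycerides; Hedges' g with a confidence interval and a log-scale triglyceride analysis would serve that purpose better.

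*Combined protocol and SAP*

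**What the plan says.** The Statistics section gives one method for every Hypothesis 3 outcome: they "will be examined using 2 time by 2 group mixed factor ANOVA with estimation of" Cohen's d. It does not state the scale of analysis, a transformation, a distribution check, which SD goes into d, a small-sample correction or a confidence interval.

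Medians and interquartile ranges appear once, for baseline description: "Participant characteristics will be reported using means/medians and standard deviations/interquartile ranges for continuous variables".

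On the role of these outcomes, Study Design says: "The tertiary outcomes of interest are scientific outcomes of initial efficacy". The Objectives add that the changes will be used to derive effect and sample sizes for a larger clinical trial, and list HbA1c, cholesterol, glucose and triglycerides as the metabolic outcomes. Insulin is among the biomarkers drawn (Study Procedures, Blood Draw) but is not in that list.

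The randomized target is "reaching recruitment goals (n=24; 12 per group) within a one-year period", with a retention goal of "retaining ≥80% of those participants through the full 16-week study period". The sample size is justified as that of a pilot "when there is no prior information for sample size estimation"; no alpha, power, SD or expected effect is given.

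**The concern.** For these outcomes the standardized effect size is the product that goes forward to the next trial. Two features of the plan bear on its quality.

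- **Small-sample bias.** Cohen's d from two small groups is biased away from zero by a known factor that depends only on the degrees of freedom. Without correction, the bias passes to the next sample size as a square.
- **Scale.** If triglycerides are right-skewed and change proportionally, an analysis of untransformed values lets the highest one or two values supply much of the SD. The test then loses efficiency, and d depends more on who happened to enrol. If the scale is not fixed in advance, it can also be chosen after the data are seen.

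At stake are the reliability of the planning estimate and some efficiency in a tertiary analysis. The primary feasibility outcomes are not affected.

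**Working it through.** **Inputs.** From the documents: 24 randomized, 12 per group. At the 80% retention goal, 0.80 × 24 = 19.2, so at least 20 completers, or 10 per arm if losses are even. There is no power calculation to reproduce. Assumed: two-sided alpha 0.05; d is the between-group difference divided by a pooled SD; and the distributions given in step 3.

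**1. Bias of d.** Hedges' factor is J = 1 − 3/(4·df − 1), with df = n1 + n2 − 2.

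| Per arm | df | J | Overstatement, 1/J | Sample size ratio, J² |
|---|---|---|---|---|
| 12 | 22 | 1 − 3/87 = 0.966 | 1.036 | 0.932 |
| 10 | 18 | 1 − 3/71 = 0.958 | 1.044 | 0.917 |

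Required sample size is proportional to 1/d². Using the uncorrected d therefore gives 1 − 0.932 = 6.8% or 1 − 0.917 = 8.3% too few participants, all else equal. For a true d of 0.50 at 12 per arm, the mean estimate is 0.50 × 1.036 = 0.52.

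**2. Imprecision of d.** The standard error is √[(n1 + n2)/(n1·n2) + d²/(2(n1 + n2))]. For d = 0.5 and 12 per arm this is √(24/144 + 0.25/48) = 0.415. The 95% interval is 0.5 ± 1.96 × 0.415, or −0.31 to 1.31.

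**3. Scale for triglycerides.** With two time points, the group-by-time test in the mixed ANOVA equals a two-sample t-test on change scores. The simulation used 12 per arm, a lognormal outcome, pre-post correlation 0.7 on the log scale and 20,000 trials per setting. It compared change in untransformed values (raw) with change in logs.

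| True reduction | Log-SD 0.4, raw / log | Log-SD 0.5, raw / log | Log-SD 0.7, raw / log | Gain from logs |
|---|---|---|---|---|
| 10% | 11.1% / 12.5% | 8.4% / 9.9% | 5.8% / 7.1% | about 1–2 points |
| 20% | – | – | – | 5–7 points |
| 30% | 62% / 77% | 42% / 58% | 22% / 34% | 12–16 points |

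For 20%, only the range of the gain is given. With no true effect, both analyses reject in about 4 to 5% of trials.

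**4. Influence of extreme values.** This is the median share of the within-group sum of squares of the 24 raw change scores:

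| Distribution | Largest value | Two largest |
|---|---|---|
| Normal | 20% | 35% |
| Lognormal, log-SD 0.5 | 27–28% | 45% |
| Lognormal, log-SD 0.7 | 32–33% | 51% |

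**5. Direction of the skew effect.** With a 30% reduction, the median absolute d is 0.93 on the log scale against 0.77 raw at log-SD 0.5, and 0.67 against 0.52 at log-SD 0.7. A next trial planned and analysed on the raw scale would need (0.93/0.77)² = 1.46 to (0.67/0.52)² = 1.66 times as many participants as one planned and analysed on the log scale. This runs opposite to step 1. They are separate effects and should not be added.

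**The case against.** **No power is claimed.** The outcomes are tertiary, no alpha or power target is set, and Type I error is sound. Even with normal data, power at 12 per arm is only 22% for d = 0.5. This stands: the plan contradicts no figure of its own, and the point is a refinement.

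**The power gain rests on the assumed effect.** The documents give no expected effect for triglycerides. At a 10% reduction the gain nearly vanishes. This stands, and is why a range is shown. The 12 to 16 points are the top of it.

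**The bias in d is trivial beside its imprecision.** At d = 0.5 it is about 0.02, against an interval from −0.31 to 1.31. This also stands. But the bias is systematic, its correction is exact arithmetic, and the interval is itself missing from the plan.

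A reader might also infer more than the documents support:

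- *That the plan commits to raw values.* It names the model and is silent on scale. Allowing medians for participant characteristics is routine and does not show that skew is expected in the outcomes.
- *That activity is near zero by design.* Eligibility requires "not engaging in regular physical activity (30 minutes accumulated per day) on more than 2 days of the week", so two such days a week are allowed. This caps regular activity and does not force zeros. Nothing shows that wrist accelerometer output sits at a floor.
- *That rank tests must replace the ANOVA for activity.* In a simulation with an assumed 30% of zeros and 12 per arm, ranks gained only 4 points over raw for a doubling of activity (19% against 15%) and 7 for a tripling (38% against 31%). A log transformation did worse than raw (11% and 19%).
- *That insulin and glucose need the same treatment.* Insulin is not a listed Hypothesis 3 outcome. For glucose, at an assumed log-SD of 0.2 and a 10% reduction, raw against log power is about 33% against 35%.

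**Conclusion.** The point holds as a minor improvement in two parts.

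The correction to d is arithmetic. Its only assumption is that d uses a between-group pooled SD with 22 or 18 degrees of freedom.

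The triglyceride part is conditional on right skew, a proportional effect, log-SD 0.4 to 0.7 and correlation 0.7, none of which the documents supply. Under those assumptions, a log-scale analysis is never worse in the settings examined and is better by about 1 to 16 points of power, depending on the true reduction. It also makes the effect size less dependent on one or two participants. The planned test is not invalid, and the documents do not support extending the criticism to the activity measures or to every biomarker.

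**What to change.** In the Statistics section:

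1. Replace Cohen's d with Hedges' g and a 95% confidence interval for every Hypothesis 3 outcome, and state which SD is used. On the pooled SD, the factor is 0.966 at 12 per arm and 0.958 at 10.
2. State that triglycerides will be analysed on the log scale and reported as a ratio of geometric means with a confidence interval. Apply this to insulin only if it is declared an outcome.
3. Keep the ANOVA for the activity questionnaires. A rank or permutation test on change can be added as a sensitivity analysis.

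The cost is a few lines of plan text and code, with no extra participants or data. The drawback is that ratios of geometric means are slightly less familiar to readers.

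### Cohen's d from 10 to 12 per arm runs about 4% high on average; reporting Hedges' g with a confidence interval is a cheap, low-severity improvement

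*Combined protocol and SAP*

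**What the plan says.** The Statistics section analyses the tertiary outcomes with a "2 time by 2 group mixed factor ANOVA with estimation of Cohen's d values for effect sizes". Of these Cohen's "d values for effect sizes" it does not say which contrast d refers to, which SD is the divisor, whether a small-sample correction is applied, or whether an interval is reported.

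The Objectives give the purpose of these outcomes: "for determining effect size and sample size estimates in powering a larger clinical trial".

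The Objectives also fix the numbers. The recruitment goal is "reaching recruitment goals (n=24; 12 per group) within a one-year period", and the retention target is "retaining ≥80% of those participants through the full 16-week study period". The 28 in the Statistics section is the number to be consented so that 12 per group are randomized. That size is defended as one that "is justified for pilot clinical trials when there is no prior information for sample size estimation". No alpha, power, target effect or SD is given.

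**The concern.** Cohen's d divides a mean difference by an SD estimated from the same small sample. The average of 1/SD over repeated samples exceeds the reciprocal of the true SD, so d is too large on average. The excess depends only on the degrees of freedom of the SD. It is a systematic error, separate from random imprecision, and it runs in the same direction for every outcome.

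It matters here because effect sizes are a stated product of the tertiary aim and are meant to inform the size of a larger trial. Required sample size varies as 1/d², so a proportional error in d roughly doubles when carried into the sample size. The correction factor is known and needs no extra data.

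**Working it through.** **The plan's own figure.** The 24 randomized rest on a pilot convention, not a power calculation, so there is no sample-size calculation to reproduce.

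**Inputs from the document.** 24 randomized, 12 per group. Retention of at least 80% means 24 × 0.80 = 19.2, so at least 20 people, about 10 per arm if losses are even.

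**Assumptions, not in the document.** d is a between-group difference divided by a pooled SD, so df = 2n − 2, which is 22 at 12 per arm and 18 at 10 per arm. Data are normal. For illustration only: two-sided alpha 0.05, 80% power, d = 0.5.

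**Step 1: bias in d.** The expected value of d is the true value divided by J, where J = Γ(df/2) / [√(df/2) · Γ((df − 1)/2)]. The usual approximation is 1 − 3/(4 df − 1).

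- 22 df: 1 − 3/87 = 0.9655 (exact 0.9655). 1/J − 1 = 3.6%.
- 18 df: 1 − 3/71 = 0.9577 (exact 0.9576). 1/J − 1 = 4.4%.

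**Step 2: sample size at the mean of d.** N is proportional to 1/d², so N from uncorrected d divided by N from corrected d is J².

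- 22 df: 1 − J² = 6.8% too small.
- 18 df: 1 − J² = 8.3% too small.

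Example with the normal-approximation formula, N per arm = 2(1.96 + 0.84)²/d². An observed d of 0.5 gives 63. Multiplying d by J gives 68 (pilot of 12 per arm) or 69 (10 per arm). If the corrected value were exactly the truth, 63 per arm would have about 77% power.

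**Step 3: sample size in a typical pilot.** N is a nonlinear function of d, so Step 2 does not describe the sample sizes such pilots would produce. The noncentral t distribution gives, for true d of 0.3, 0.5 and 0.8:

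| | 12 per arm | 10 per arm |
|---|---|---|
| Median of d above truth | 1.1–1.2% | 1.4% |
| Median N from d | 2.3% too small | 2.7–2.8% too small |
| Median N from g = J·d | about 5% too large | about 6% too large |

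Medians of N count non-positive estimates as unboundedly large.

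**Step 4: bias against noise.** With true d = 0.5:

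- 12 per arm: mean d is 0.518 and its sampling SD 0.436. The bias of 0.018 is 0.018/0.436 = 4% of one SD.
- 10 per arm: mean d is 0.522 and its sampling SD 0.483. The bias of 0.022 is about 5% of one SD.
- The 95% interval for an observed d of 0.5 is about -0.32 to 1.31 at 12 per arm and -0.40 to 1.38 at 10 per arm.
- At 12 per arm, the middle half of pilot estimates implies between about 25 and 307 per arm, against 63 needed.

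**Step 5: is g the better estimator?** g is unbiased for the standardized difference. Its mean squared error at true d = 0.5 is lower than that of d by about 7% (12 per arm) to 8.5% (10 per arm).

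**The case against.** The strongest reply is that the correction changes no decision. The bias is about 0.02 against a sampling SD of 0.44 to 0.48, the outcomes are tertiary, and the plan gives no rule for turning d into a sample size. This stands, and it is why the point ranks low. It is not a reason to keep a known bias when the alternative costs nothing and has lower mean squared error.

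A reader might infer that the next trial would come out 7% to 8% too small, or would have 77% power instead of 80%. Neither follows. Both figures describe the sample size at one fixed or average value of d. In the median pilot the shortfall is 2% to 3%. By the same measure g overshoots, with a median N about 5% to 6% too large. Hedges' g is unbiased for the effect, not for the sample size.

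A reader might also infer that the plan has chosen an uncorrected d. The text is silent on any correction and does not rule one out. Nor does it define the contrast. If d were a within-arm pre-post value (11 to 9 df), the Step 2 figure would be 13.5% to 16.5%. The percentages above therefore hold only for the between-group reading.

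**Conclusion.** The point holds as a cheap improvement of low severity. With a between-group, pooled-SD d on 22 to 18 df, Cohen's d is 3.6% to 4.4% too large on average, and Hedges' g removes that bias. The percentages do not depend on the assumed alpha or power, apart from rounding, but they do depend on the assumed contrast and standardizer.

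The effect on sample size is modest: 6.8% to 8.3% at the mean of d, and about 2% to 3% at the median. Imprecision is the much larger problem for anyone sizing a trial from these data, and the correction does not touch it. This is an unspecified detail, not an internal contradiction, and the primary feasibility and secondary acceptability results are unaffected.

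**What to change.** In the Statistics section, state that the effect size is Hedges' g, that is d multiplied by 1 − 3/(4 df − 1), for the between-group difference in change from baseline to post-test. Name the standardizer and report a 95% confidence interval. Give g in place of Cohen's d or beside it. Carry g with its interval, not the uncorrected point estimate alone, into any sample-size work for the larger trial.

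The cost is a sentence or two of wording, one multiplication per outcome and an interval; no further participants or data are needed. The downside is that reported effects become about 4% smaller. The text should also say that the pilot estimate, corrected or not, is too imprecise to size the next trial on its own.
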